7.8 Unscheduled Visits

Assessments completed during an unscheduled visit will be recorded on the applicable eCRFs.

7.9 Early Withdrawal/Premature Discontinuation of Subjects

Subjects may be withdrawn early from the study for several reasons including:

- Subject death
- Subject lost to follow-up

- Subject request for withdrawal (withdrawal of consent)
- Adverse event
- Investigator decision

If a subject is withdrawn from the study early, a Study Completion CRF must be completed to describe the reason for early withdrawal. The investigator should make all attempts to conduct an "Early Withdrawal" visit at the time of the withdrawal from the study. If a subject has withdrawn consent for the study or is lost to follow-up, the completion of this visit is not imperative. In situations where study withdrawal is due to an adverse event, subjects will be followed until resolution of the adverse event or determination that the subject's condition is stable.

If a subject chooses to withdraw from the study and also withdraws consent for disclosure of further information, no further study assessments should be performed, and no additional data collected. The sponsor may retain and continue to use any data collected prior to the withdrawal of consent.

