5.0 ENDPOINTS

5.1 Primary Safety Endpoint

The primary safety endpoint for the study is the occurrence of MACCE at 30 days, defined as a composite of the following VARC-2 defined components:

- All-cause mortality
- All stroke (disabling and non-disabling)
- Acute kidney injury (AKI) Stage 2 or 3 (including renal replacement therapy) within 72 hours

5.2 **Primary Performance Endpoint**

The primary performance endpoint for the study is device procedural success, defined as successful insertion, deployment, positioning, and removal of the EmStop System in the absence of device interference.

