7.3 Point of Enrollment & Numbering of Study Subjects

A patient will be considered enrolled as a study subject once an investigational EmStop System has entered the subject. The lowest available subject number will be assigned, progressing sequentially for each enrolled subject thereafter. The CRO will be notified of subject enrollment via the electronic data capture (EDC) database.

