8.0 STATISTICAL METHODS

8.1 Analysis Data Sets

The primary analysis will consist of all available data on all subjects enrolled, referred to in ICH E9 ("Statistical Principles for Clinical Trials") as the full analysis set. As the study is a treatmentonly, single arm design, summaries of results will principally be presented for the entire study population.

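### After withdrawal for an adverse event or by investigator decision, Section 7.9 does not secure day-30 status, so a later death or stroke may go uncollected for 30-day MACCE

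*Combined protocol and SAP*

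**What the plan says.** The endpoint is fixed in time. Section 5.1: "The primary safety endpoint for the study is the occurrence of MACCE at 30 days". Its components are all-cause death, all stroke, and "Acute kidney injury (AKI) Stage 2 or 3 (including renal replacement therapy) within 72 hours".

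Every enrolled subject has been exposed. Section 7.3: "A patient will be considered enrolled as a study subject once an investigational EmStop System has entered the subject". Under Section 7.5 the device is taken out at the end of the TAVR procedure.

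Section 7.9 deals with leaving the study, not with stopping treatment: "Subjects may be withdrawn early from the study for several reasons including" death, loss to follow-up, withdrawal of consent, an adverse event, and "Investigator decision". For the adverse-event route it adds "In situations where study withdrawal is due to an adverse event, subjects will be followed until resolution of the adverse event", with the subject being judged stable as an alternative end point. For any early withdrawal it asks the investigator to try to hold a visit when the subject leaves. It gives no criteria for withdrawal by the investigator and names no contact after that visit.

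On analysis, Section 8.1 says "The primary analysis will consist of all available data on all subjects enrolled", Section 8.3 makes the safety summary descriptive, and Section 8.9 leaves missing data to the SAP.

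**The concern.** Once the device is out, no study treatment remains to be discontinued. Withdrawal for an adverse event or by investigator decision then ends study assessments, and as written it can end outcome collection with them. The follow-up that Section 7.9 keeps is tied to one event or to the day of leaving, not to day 30. A subject can be declared stable in the first or second week, leave, and then die or have a stroke before day 30 with no rule that obliges the site to find out.

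Withdrawal for an adverse event is not random: it selects subjects who have been unwell. If later events among them are missed, the 30-day MACCE proportion is understated. The study exists to characterise safety and to inform a pivotal trial (Sections 6.1 and 8.8), and with 15 subjects a single missed event is visible in the result.

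**Working it through.** **Step 1. What follow-up does each route guarantee?**

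| Route out of the study | Follow-up required | Day-30 status secured? |
|---|---|---|
| Adverse event (7.9) | Until that event resolves or the subject is stable, plus an attempted exit visit | No; either can come before day 30 |
| Investigator decision (7.9) | Attempted exit visit at the time of leaving | No |
| Lost to follow-up (7.10) | Three telephone attempts, then a certified letter | Sought |

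A subject whom the investigator withdraws is thus pursued less than one who cannot be reached.

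**Step 2. Which components are exposed?** Death and stroke run to day 30. AKI is settled within 72 hours, so it is at risk only if withdrawal falls inside that window. A stroke or AKI that itself prompts withdrawal is already recorded, and death is itself an endpoint event. The open class is therefore a new death or stroke after withdrawal and before day 30. (Section 13.2 adds TIA to MACCE, unlike Section 5.1; if that definition governs, later TIA belongs here too.)

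**Step 3. Size.** The plan states no figure to reproduce: Section 8.8 does not base the sample size on power, and no withdrawal rate is given. Inputs:
- n = 15 (Section 8.8).
- k = subjects withdrawn before day 30 without a prior MACCE and with unknown day-30 status. *Assumption:* 1 to 3.
- x = MACCE observed. *Assumption:* 0 or 1.

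Best case = x/15. Worst case = (x + k)/15. Known status only = x/(15 − k).

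| k | x | Known status only | Best case | Worst case |
|---|---|---|---|---|
| 1 | 0 | 0/14 = 0% | 0/15 = 0% | 1/15 = 6.7% |
| 1 | 1 | 1/14 = 7.1% | 1/15 = 6.7% | 2/15 = 13.3% |
| 2 | 0 | 0/13 = 0% | 0/15 = 0% | 2/15 = 13.3% |
| 2 | 1 | 1/13 = 7.7% | 1/15 = 6.7% | 3/15 = 20.0% |
| 3 | 0 | 0/12 = 0% | 0/15 = 0% | 3/15 = 20.0% |
| 3 | 1 | 1/12 = 8.3% | 1/15 = 6.7% | 4/15 = 26.7% |

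Exact (Clopper-Pearson) 95% intervals:
- 0/15: 0 to 21.8% (upper limit 1 − 0.025^(1/15) = 0.218)
- 1/15: 0.2 to 31.9%
- 2/15: 1.7 to 40.5%
- 0/14: 0 to 23.2%
- 0/13: 0 to 24.7%

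**Step 4. How much is one event worth?** Section 2.0 cites 3.8% cerebrovascular events at 30 days in a large TAVR trial. That is not a MACCE rate and serves only as a scale. At 3.8%, expected events = 15 × 0.038 = 0.57; P(at least 1) = 1 − 0.962^15 = 0.44; P(at least 2) = 0.11. One missed event could be the whole observed signal.

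**The case against.** The protocol does not ignore follow-up. Section 7.0 asks that subjects attend all scheduled visits to avoid missing data. Section 7.10 calls for every effort to complete the schedule, whereas Section 7.9 only permits withdrawal. Section 11.2 follows all adverse events to resolution or stability and requests documents for any death. A loss needs a chain: withdrawal for something other than MACCE, resolution or stability before day 30, then a new death or stroke that the site never hears of. The study is descriptive, so no test or success rule is affected, and the intervals above overlap heavily.

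Most of this stands and limits the weight of the point. It does not close the gap. Section 7.0 itself refers withdrawal to the later section, the contact steps in 7.10 are written for subjects lost to follow-up, and 11.2 has the same early end point as 7.9.

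Three stronger readings are tempting and are not supported:
- *That such subjects are dropped from the analysis or counted as event-free.* Section 8.1 defines an analysis set only. Section 8.9 sends missing data to a SAP whose text is not in the material reviewed, so the absence of a method is not held against the plan. No method, however, can recover an event that was never collected.
- *That the two withdrawal reasons serve no purpose and should go.* Study burdens continue after the device is out (MRI at 18-36 hours, laboratory tests, cognitive and functional scales, a clinic visit), and an investigator may have reason to end them. The list is also introduced as non-exhaustive, so deleting entries would prohibit nothing.
- *That listing death as a withdrawal reason removes it from the endpoint.* All-cause mortality is a MACCE component in Sections 5.1 and 13.2; its place in 7.9 is a disposition category.

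**Conclusion.** The gap is real but narrow. Section 7.9 allows exit from the study before day 30 by two routes with no duty to establish day-30 status, and the general statements elsewhere reduce the risk without removing it. What may be missed is a later death or stroke, not the event that led to withdrawal.

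With no other events, one withdrawn subject leaves the 30-day proportion undetermined between 0% and 6.7%, and two between 0% and 13.3%. These ranges rest on an assumed number of withdrawals. They show what could be hidden, not what is expected: a withdrawn subject may well have no later event. The consequence is an incomplete and possibly low safety estimate, not an error in a test. This is a cheap improvement.

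**What to change.** In Section 7.9, separate stopping study assessments from stopping outcome collection. State that, whatever the reason for withdrawal, day-30 vital status and stroke/MACCE status will be obtained, by telephone or from records if there is no visit, for every enrolled subject who has not withdrawn consent to further data collection. Reconcile this with Sections 7.0 and 7.10. The listed withdrawal reasons can stay.

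In Section 8.3, keep all enrolled subjects in the denominator and show best-case and worst-case results for anyone whose day-30 status is still unknown, consistent with the SAP's missing-data section. A denominator limited to subjects with known status would report 0/14 and hide the uncertainty.

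With full ascertainment the range closes to one value, for example 0/15 (0 to 21.8%) or 1/15 (0.2 to 31.9%). The sample size does not change. The cost is a wording change and, for at most 15 subjects, a few calls or record checks. It concerns data collection only.

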7.10 Handling Subjects Lost to Follow-Up

Every attempt must be made to have all subjects complete the follow-up visit schedule. A subject will be considered lost-to-follow-up when all efforts to obtain compliance are unsuccessful. At a minimum, the effort to obtain follow-up information must include three attempts to make contact via telephone, and if contact via phone is not successful, a certified letter from the principal investigator (PI) or authorized delegate must be sent to the subject's last known address. Both telephone and letter contact efforts to obtain follow up must be documented in the subject's medical records and on the Study Completion eCRF.

7.11 Handling of Samples Obtained from Subjects

No subject samples will be retained by the sponsor.

8.0 STATISTICAL METHODS

8.1 Analysis Data Sets

The primary analysis will consist of all available data on all subjects enrolled, referred to in ICH E9 ("Statistical Principles for Clinical Trials") as the full analysis set. As the study is a treatmentonly, single arm design, summaries of results will principally be presented for the entire study population.

8.2 General Statistical Principles

Continuous data will be summarized using the following descriptive statistics: mean, standard deviation, median, and range or interquartile range. Categorical variables will be summarized using frequency counts and percentages. For events that can occur more than once in a single

subject, such as adverse events (AEs), the percentage will be based on the number of subjects experiencing the event; both subject and event counts will be reported.

All statistical analyses will be performed using SAS (version 9.4 or higher, SAS Institute Inc. Cary, NC), R (version 3.2 or higher, R Foundation for Statistical Computing, Vienna, Austria) or other widely accepted statistical or graphical software.

8.3 Analysis of Primary Safety Endpoint

The primary safety endpoint will be summarized descriptively per the general statistical principles described above. The intent of this analysis is to capture, characterize, and report safety outcomes associated with the use of the EmStop System.

8.4 Analysis of Primary Performance Endpoint

The primary performance endpoint will be summarized descriptively per the general statistical principles described above. The intent of this analysis is to capture, characterize and report performance outcomes associated with the use of the EmStop System.

8.5 Analysis of Secondary Endpoints

Secondary endpoints will be summarized descriptively per the general statistical principles described above.

8.6 Safety Analysis

Summary tables and listings will be provided for all reported adverse events, which will additionally be reported by seriousness and relatedness. Such summaries will comprise the number and percentage of subjects with an adverse event and the total number of such events. The proportion of subjects with events will be considered primary for analysis of adverse events.

8.7 Subgroup Analysis: Learning Curve

As it is plausible that a learning curve will be observed in the use of this novel technology, to assess the effect of operator experience on outcomes, subgroup analyses of the primary endpoints distinguishing the first from all subsequent subjects per attending physician will be performed.

8.8 Sample Size

The sample size of 15 was selected to provide clinical and statistical information, including assessment of point estimates, frequencies, and variability in key outcomes, to inform design elements of a subsequent pivotal study.

As the objective of this investigation is to characterize outcomes under treatment, sample size is not driven by formal evaluations of power against predefined success criteria. Where performed, hypothesis testing will have one-sided tests with p-values less than 0.025 deemed significant and two-sided tests with p-values less than 0.05 deemed significant.

8.9 Statistical Analysis Plan

Refer to the Statistical Analysis Plan (SAP) for details on statistical design, method and analytical procedures including testing of poolability across clinical sites and handling of missing data.

9.0 MEASURES TO AVOID & MINIMIZE BIAS

The study has several measures that have been implemented to avoid and minimize bias, including the following: use of an independent CRO for study operations management, monitoring, and data management; identification of an independent medical monitor; and use of an independent pathology core laboratory and independent MRI reader for systematic review of the debris captured by the EmStop System and study MRIs, removing any potential for investigator bias.

9.1 Medical Monitor

A Medical Monitor with clinical expertise in TAVR procedures will oversee and evaluate safety events to provide formal safety monitoring and independent, objective expert counsel for this feasibility study. The Medical Monitor will follow pre-specified guidelines to adjudicate AEs and adjudicate them for seriousness and relatedness. In addition, the Medical Monitor may advise the sponsor regarding the continuing safety of study subjects and those yet to be recruited. Sites will be expected to provide supporting source documentation, as requested, to assist the Medical Monitor with evaluation of safety-related events. Core Laboratory

A pathology core laboratory will be used to provide an unbiased assessment of debris samples collected for processing and analysis. The pathology core laboratory will provide shipping and processing instructions to the sites. The pathology core laboratory will follow its own charter or similar procedure to systematize their image review in compliance with the study protocol.

10.0 BENEFITS & RISK ANALYSIS

10.1 Potential Benefits of Study Participation

There are no guaranteed benefits from participation in this study; however, it is possible that treatment with a study device may have the following benefits:

• Reduced risk of stroke

10.2 Alternative Treatment

There is no obligation for a patient to take part in this study. Alternative treatments may include:

- TAVR without embolic protection
- TAVR with embolic protection using a commercially available device (e.g., Boston Scientific SENTINEL)

10.3 Potential Risks Associated with Study Participation

As with any percutaneous coronary procedure, use of the study devices during TAVR involves some risks. Risks associated with laboratory testing (i.e., blood draws) and the TAVR procedure will be listed in the site's procedure consent form used per their standard of care. Potential risks associated with the EmStop System may include but are not limited to:

- Acute kidney injury (AKI)
- Atrial fibrillation (new or worsening)
- Bleeding (life-threatening, major, minor)
- Death
- Periprocedural myocardial infarction (MI)
- Stroke
- Transient ischemic attack (TIA)
- Vascular or access-related complications

The frequency and severity of adverse events can vary, and may necessitate additional medical intervention, including surgery.

10.4 Methods to Minimize Risks

The EmStop System was subjected to a risk assessment as part of the design control process. Results of pre-clinical bench and laboratory testing have demonstrated that the device is likely to be safe and perform as intended in clinical use.

During this study, risks will be further minimized through careful subject screening and selection, training of investigators and study staff, adherence to the scheduled assessments, and regular monitoring visits.

10.5 Benefit-to-Risk Rationale

The results from risk analysis and risk mitigation measures support reasonable assurance of the safety and efficacy of the EmStop System when used in a manner consistent with its labeling and intended use. The evidence supporting safety and effectiveness of the EmStop System is based on robust pre-clinical bench and laboratory testing, as well as the clinical experience of similar TAVR embolic protection products, such as the market-released SENTINEL (Boston Scientific). The evidence supports a clinical benefit-to-risk determination that is favorable for the EmStop System.

11.0 ADVERSE EVENTS

11.1 Adverse Event Definitions

Adverse events will be adjudicated for seriousness and for relatedness to the investigational device and study procedure. Refer to **Section 13.0** for adverse event definitions.

11.2 Adverse Event Collection & Documentation

Collection of adverse events will start on the day of the procedure for enrolled subjects and will be assessed and reported throughout the study. Investigators must obtain all information available to determine the seriousness, relatedness, and outcome of the adverse event and to assess whether it meets the criteria for classification as an unanticipated adverse device effect (UADE) requiring immediate notification. All adverse events will be followed until resolution or investigator determination that the subject's condition is stable.

All reported adverse events will be documented on the Adverse Event CRF. Copies of deidentified source documentation that contain significant information related to the event, such as progress notes, consultations, nurse notes, operative reports, and subject summaries may be requested by the sponsor, CRO, Medical Monitor and/or core lab as needed for evaluation and adjudication.

The following are not considered reportable adverse events for this study:

- Any normal expected postoperative complaints or symptoms unless the event involves a clinically significant change in severity or duration of symptoms or requires clinical intervention that is different from ordinary postoperative care. Expected postoperative complaints and findings include, but are not limited to headache, edema, nausea, vomiting, and postoperative pain (excluding chest pain).
- Any condition that is recorded as pre-existing at baseline, unless there is a worsening of that condition in terms of nature, severity, or degree of incidence.
- Planned hospitalization for pre-existing conditions or a procedure required by the protocol, without serious deterioration in health.

In case of subject death, it is requested that a copy of the death certificate and a copy of the autopsy report, if applicable, be sent to the CRO. Any other source documents related to the death should also be provided to the CRO. If no source documents are available, the PI is required to describe the circumstances of the subject's death in written communication (e.g., letter, e-mail).

11.2.1 Device Deficiencies

Device performance, including deficiencies, will also be collected. If a device deficiency results in the subject experiencing any untoward medical occurrence, unintended disease or injury, or untoward clinical signs, these outcomes will be reported as an adverse event on an Adverse Event CRF. Any malfunctioning devices will be returned to the sponsor by the site for further evaluation.

11.3 Adverse Event Reporting Timeframes

The investigator is responsible for reporting serious adverse events to the IRB in accordance with the IRB's procedures. Unanticipated adverse device effects (UADEs) have special reporting requirements for both the investigator and sponsor, as described in 21 CFR 812.150:

- **Investigator Report:** If a subject experiences a UADE, the investigator must notify the sponsor/CRO and the reviewing IRB as soon as possible, but no later than 10 working days after the investigator first learns of the effect.
- **Sponsor Report:** UADEs will be reported to the FDA, all reviewing IRBs, and participating investigators as soon as possible, but no later than 10 working days after receiving notice of the UADE.

11.4 Adverse Event Relatedness

The investigator and the Medical Monitor will assess the relatedness of the adverse event to the investigational device and the study procedure using the categories listed below (see **Section 13.0** for definitions):

- Definitely
- Probably
- Possibly
- Unlikely
- Not Related

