6.5.3 General Exclusion Criteria

Subjects must not meet any of the following exclusion criteria:

- 1. Requires urgent or emergent TAVR procedure
- 2. Contraindicated to MRI
- 3. Previously implanted aortic or mitral valve bioprosthesis
- 4. Hepatic failure (Child-Pugh class C)
- 5. Hypercoagulable state that cannot be corrected by additional periprocedural heparin
- 6. Planned to undergo any other cardiac surgical or interventional procedure (e.g., concurrent coronary revascularization) during the TAVR procedure or within 30 days prior to the TAVR procedure. NOTE: Diagnostic cardiac catheterization is permitted up until baseline MRI is obtained. Once baseline MRI is obtained, no additional intra-aortic or intracardiac procedure may occur.
- 7. Acute myocardial infarction within 30 days of the planned index procedure
- 8. Renal failure, defined as estimated glomerular filtration rate (eGFR) <30 mL/min
- 9. Documented history of stroke or TIA within the prior 6 months, or any prior stroke with a permanent major disability or deficit (NIHSS >1 at baseline)
- 10. Left ventricular ejection fraction ≤30% within 3 months prior to procedure
- 11. History of intolerance, allergic reaction, or contraindication to any of the study medications, including heparin, aspirin, clopidogrel, or a sensitivity to contrast media or anesthesia that cannot be adequately pre-treated
- 12. Known allergy or sensitivity to nickel-titanium
- 13. Active endocarditis or ongoing systemic infection, defined as fever (>38°C) and/or white blood cell (WBC) >15,000 IU

- 14. Undergoing therapeutic thrombolysis
- 15. History of bleeding diathesis or a coagulopathy
- 16. Known or suspected to be pregnant, or is lactating; female subjects of child-bearing potential must have a negative serum or urine pregnancy test within 48 hours prior to the index study procedure.
- 17. Currently participating in another drug or device clinical study
- 18. Any other clinical reason, as deemed by the investigators of the study, by which the patient would not be an appropriate candidate for the study
- 19. Vulnerable subject populations (e.g., incarcerated or cognitively challenged adults)

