13.0 DEFINITIONS

13.1 Adverse Event Definitions

Adverse event (AE): Untoward medical occurrence, unintended disease or injury, or untoward clinical signs (including abnormal laboratory findings) in subjects, users, or other persons, whether or not related to the investigational medical device and whether anticipated or unanticipated. [*ISO 14155 2020, 3.2*]

Adverse event relatedness: The relationship of an adverse event to the investigational device or the study procedure based on the categories defined below.

Relatedness	Description
Definitely	The adverse event follows a strong temporal sequence to the receipt (or attempted receipt) of the device treatment or procedure. This can include an adverse event that occurs after the study procedure.
Probably	The adverse event follows a reasonable temporal sequence to the receipt (or attempted receipt) of the device treatment or procedure, and the possibilities of other factors, such as underlying and concomitant illness, concomitant medications, or concurrent treatment can be excluded.
Possibly	The adverse event follows a reasonable temporal sequence from receipt (or attempted receipt) of the device treatment or procedure and the possibility of device treatment or procedure involvement cannot be excluded. However, other factors such as underlying or concomitant illness, concomitant medications, or concurrent treatment are presumable.
Unlikely	The adverse event has an improbable temporal sequence to the receipt (or attempted receipt) of the device treatment or procedure, or it can be reasonably explained by other factors, including underlying or concomitant illness, concomitant medications, or concurrent treatment.
Not related	The adverse event has no temporal sequence to the interventional procedure, the device treatment, or any user handling, or it can be explained by other factors, including underlying disease or concomitant illness, concomitant medication, or concurrent treatment.

Device deficiency: Inadequacy of a medical device with respect to its identity, quality, durability, reliability, usability, safety, or performance. [*ISO 14155 2020, 3.19*]

• Note: Device deficiencies include malfunctions, use errors, and inadequacy in the information supplied by the manufacturer including labelling. This definition includes device deficiencies related to the investigational medical device or the comparator.

Serious adverse event (SAE): An adverse event that led to any of the following:

- Death

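### Adverse events are rated against the EmStop device and an undefined 'study procedure' with no rating for the concurrent TAVR, so procedure-related harm cannot be divided between the two and the device rating is weakened

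*Combined protocol and SAP*

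**What the plan says.** Three sections name the targets of attribution, and all name the same two. Section 11.1: "Adverse events will be adjudicated for seriousness and for relatedness to the investigational device and study procedure". Section 11.4: "The investigator and the Medical Monitor will assess the relatedness of the adverse event to the investigational device and the study procedure". Section 13.1 defines relatedness as "The relationship of an adverse event to the investigational device or the study procedure based on the categories defined below".

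The definitions in 13.1 and 13.2 do not include 'study procedure'. The five categories in 13.1 form one set that serves both targets. The criterion for 'Definitely' is "The adverse event follows a strong temporal sequence to the receipt (or attempted receipt) of the device treatment or procedure". 'Probably' is stricter on causes: it asks that other factors "such as underlying and concomitant illness, concomitant medications, or concurrent treatment can be excluded".

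On reporting, 8.6 says "Summary tables and listings will be provided for all reported adverse events, which will additionally be reported by seriousness and relatedness". It does not say whether the investigator's or the Medical Monitor's rating is tabulated, or whether the two targets are cross-tabulated.

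Section 10.3 does distinguish the treatments. It leaves TAVR risks to the site's procedure consent form and opens a separate list with "Potential risks associated with the EmStop System may include but are not limited to".

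**The concern.** Sections 3.2, 6.1 and 7.5 describe one session in which a marketed valve is delivered through the EmStop filter sheath, by the same femoral access. Every subject gets both treatments, and there is no control arm. The stated objective in 4.0 is to demonstrate the safety of EmStop, so the judgement on each event's cause has to carry much of the distinction between EmStop harm and ordinary TAVR harm.

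A two-target scheme with one target undefined does this poorly. An injury from advancing or withdrawing EmStop and an injury from the valve procedure can both end up as procedure related. Two sites may also read the term differently and rate like events differently. The results are meant to inform a pivotal study (8.8), which would inherit the ambiguity. So does Table 3 in 12.1.4, where expedited reporting of incomplete resheathing, retraction or bail-out depends on whether a resulting event is device or procedure related.

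**Working it through.** The plan states no figure on this point, so there is nothing to reproduce. The check is a reading of the text, followed by a short calculation of whether rates could replace attribution.

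**1. What each target covers.**

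| Target | Meaning in the protocol | Separates EmStop from TAVR? |
|---|---|---|
| Investigational device | EmStop only (3.1, 12.3): introducer sheath, delivery catheter, filter sheath | In part |
| Study procedure | Not defined | No |
| TAVR valve or procedure | Not a target | Not applicable |

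**2. What 'study procedure' might mean.** Exclusion 16 in 6.5.3 times a pregnancy test "within 48 hours prior to the index study procedure", and Table 2 has a single treatment-procedure column. Both suggest the whole session. Against that, exclusion 6 and section 7.5 name the TAVR procedure separately. Neither reading is settled by the text.

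**3. One event taken through the 13.1 categories.** Suppose a complication during the session that in truth arises from valve deployment, rated against the device.

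- 'Definitely': met. The timing relative to the device treatment or procedure is strong, and nothing about other causes is required.
- 'Probably': not met if TAVR counts as concurrent treatment, since that cannot be excluded. The text does not say whether it counts.
- 'Unlikely' and 'Not related': each can be met through its second limb, which applies when concurrent treatment explains the event.

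The same event can thus qualify for both ends of the scale. The cause is that 'Definitely' asks for less than 'Probably' does, and that the wording joins device treatment and procedure with 'or'.

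**4. Could rates do the separating?** Inputs: n = 15 (6.2 and 8.8; enrolment is up to 15). Background rates p from section 2.0 are 3.8% for cerebrovascular events at 30 days and 4.1% for stroke in the first 10 days. Assumptions: independent subjects, rates that apply to this population, and no effect of EmStop.

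- Expected events = 15p: 15 × 0.038 = 0.57; 15 × 0.041 = 0.62.
- P(at least one) = 1 − (1 − p)^15: 1 − 0.962^15 = 44%; 1 − 0.959^15 = 47%.
- P(at least two) = 1 − (1 − p)^15 − 15p(1 − p)^14: 11% and 12%.
- For more frequent complications the documents give no rate. At assumed rates of 5%, 10% and 20%, P(at least one) is 54%, 79% and 96%.
- Exact 95% intervals: 0/15 gives 0% to 21.8%; 1/15 gives 0.2% to 31.9%.

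A background event is about as likely as not even for stroke, and the intervals are too wide to tell an EmStop excess from background. The task falls to event-level attribution.

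**5. Whose rating.** Section 11.4 has two raters. Sections 9.1 and 11.1 speak of adjudication, and 9.1 gives it to the Medical Monitor. Section 8.6 does not carry this into the tables.

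**The case against.** The strongest reply is that the device target already is the EmStop attribution. The System comprises the introducer sheath, delivery catheter and filter sheath, so an injury from inserting or withdrawing them can be rated to the device. This stands. A reader might infer that the plan cannot separate EmStop harm from TAVR harm at all; the documents do not support that. A reader might also take it as stated that 'study procedure' includes the TAVR; that is a natural inference, but only an inference.

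Other parts of the reply also stand. EmStop-specific problems are recorded elsewhere: device deficiencies (11.2.1), device interference as part of the performance endpoint (5.2, 13.2), and filter retraction and bail-out use (5.4). Section 8.6 promises listings, and with at most 15 subjects each event can be read individually. The Medical Monitor's guidelines (9.1) and the separate plan cited in 8.9 were not in the file reviewed and may hold further rules.

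Two parts do not stand. The 13.1 categories do not resolve the competing cause, since step 3 shows that they can admit opposite answers for one event. And rules held only in the Monitor's guidelines would not reach the investigators, who also rate under the protocol.

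It is fair to add that, with one session and one access, some events cannot be attributed by anyone. Extra fields will not change that, but they will show how many such events there are.

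**Conclusion.** The point holds in limited form. The device rating gives some attribution to EmStop, but procedure-related events cannot be split between EmStop steps and TAVR. The device rating is weakened by a top category that rests only on timing shared by both treatments. It is a recommended improvement to the safety characterisation and does not invalidate the study.

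The primary MACCE endpoint in 5.1 is untouched, because death, stroke and AKI count whatever their cause. What is affected is the relatedness tables under 8.6. The size cannot be given as a number of events, because the documents supply no expected count of procedure-related events; only the exposure is known, and it is every subject. The 44% to 47% figure shows why attribution matters and rests on the assumptions in step 4; it does not measure misclassification. The conclusion would soften if the Medical Monitor's guidelines or the adverse event form already define the term or carry a TAVR field.

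**What to change.** In 11.1, 11.4, 13.1 and the adverse event form:

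- Define 'study procedure', and use the defined term in Table 3 as well.
- Rate each event separately for (a) the EmStop device, (b) EmStop-specific procedural steps and (c) the TAVR device or procedure. Allow more than one target, and add an entry for events that are indeterminate between EmStop and TAVR.
- Apply the 13.1 categories to each target on its own. State that TAVR counts as concurrent treatment when EmStop is rated, and require that 'Definitely' take alternative causes into account.

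In 8.6, tabulate each target and the overlap between targets on the Medical Monitor's adjudicated rating, and list disagreements with the investigator.

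The cost is one or two extra form fields, some table columns and a wording amendment, with no new visits. The downside is that some events will remain indeterminate, and the tables will say so openly.
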